## 6. RATIONALE AND BACKGROUND

Patients with chronic obstructive pulmonary disease (COPD) have been demonstrated to have an increased risk of pneumococcal disease. Pneumonia is frequent among patients hospitalized for COPD exacerbations and is associated with increased health care utilization and higher mortality. Nonpneumonic COPD exacerbations predict increased risk of subsequent exacerbations. Among community acquired pneumonia (CAP) patients with the highest severity of disease who require hospitalization, COPD is the most common comorbidity. These two diagnoses, CAP and acute exacerbations of COPD (AECOPD), come together when COPD patients acquire AECOPD caused by CAP.

Exacerbations are a significant component of the clinical course in COPD. Furthermore, as COPD progresses, exacerbations become more frequent. COPD exacerbations are defined as a complex of two or more respiratory symptoms (worsening dyspnea, cough, sputum production, chest tightness, or wheezing) related to the underlying COPD, with duration of 3 days or more, that require a change in treatment. Acute exacerbations of COPD (AECOPD) have a great impact on health status, disease progression, and prognosis. Up to 50%–70% of AECOPD can be attributed to respiratory infections by viruses or bacteria, even more in the most severe patients. They are often associated with the colonization of airways by multiple bacteria or viruses of low virulence that in normal conditions are parts of the normal flora of the upper airway.

Some studies have identified factors independently associated with bacterial growth, such as current smoking and *H. influenzae*; longer periods between exacerbations and *S. pneumoniae*; or decrease in FEV1 and *P. aeruginosa*. Traditionally, bacterial identification has been defined depending on the severity of the COPD, since *S. pneumoniae* and *M. catharralis*, are isolated in patients with predicted FEV1 >50%, and *H. influenzae*, Enterobacteriaceae and *P. aeruginosa* in those with FEV1 <50%.

Therefore, considering *S. pneumoniae* appears to be more frequent in patients with mild/moderate COPD, these subjects might be the most benefited from a preventive approach targeting this pathogen.

Redacted

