## 7. RESEARCH QUESTION AND OBJECTIVES

- **Primary objectives**

1. Evaluate the impact of routine clinical practice vaccination with PCV13 on the reduction of the risk of COPD moderate/severe exacerbations (see definitions) in adults, after 2 years of follow up.
2. Determine which subgroup of patients (based on the severity of COPD) benefit most from vaccination with PCV13  
COPD severity (GOLD)
  - GRADE 1: Mild/unknown [FEV1≤ 80%, FEV1/FVC < 0,7 or no spirometry data]
  - GRADE 2: Moderate [50% ≤ FEV1< 80%, FEV1/FVC < 0,7]
  - GRADE 3: Severe [30% ≤ FEV1 < 50%, FEV1/FVC < 0,7]
  - GRADE 4: Very severe [FEV1< 30% o FEV1< 50% plus respiratory failure, FEV1/FVC < 0,7])

- **Secondary objectives**

1. Evaluate the impact of influenza and PCV13 vaccination on the reduction of the risk of exacerbations
2. Evaluate the impact of vaccination with PCV13 on patients' quality of life
3. Evaluate the impact of vaccination with PCV13 on the decrease of FEV1
4. Estimate the potential economic savings for the healthcare system derived from vaccination of COPD patients with PCV13
5. Determine the prevalence of PCV13 vaccination in COPD patients.

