#### **8.5. Study size**

With 35% patients vaccinated with PCV13, enrolling 1540 eligible COPD patients will provide approximate 540 patients in PCV13 cohort and 1000 patients in the control cohort.

Assuming 37% of the control patients experiencing moderate/severe exacerbation per year with 70% of the patients remaining in the study at year 1, this sample size will provide 91% power to detect a statistical significant reduction of 10% on COPD moderate/severe exacerbations from PCV13 after 1-year. Assuming additional 30% dropout from year 2, the study sample size will provide 91% power to detect a statistical significant reduction of 14% on COPD moderate/severe exacerbations from PCV13 after 2-year.

Time	PCV13		Control		Power	Retention Rate
	Sample Size	% exacerbation	Sample Size	% exacerbation		
Enrollment	540		1000			
1-year	378	27%	700	37%	91.43%	70% from Enrollment
2-Year	264	60%	490	74%	91%	70% from Year 1

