### **8.9. Limitations of the research methods**

- The actual proportion of subjects who would follow their healthcare practitioner (HCP) vaccination recommendation is not known, so this aspect might influence the size of the vaccinated group and therefore the global results.
- Losses to follow-up can introduce bias in the global results obtained.
- Considering the bacterial etiology depending on disease severity, a very large percentage of patients with  $FEV_1 < 40\%$ , would limit the proportion of *S.pneumoniae* presence in the study population and hence the potential impact of the immunization.
- The estimated study sample, aims to determine if there is a 10% significant reduction on the risk of all cause COPD exacerbations in PCV13 vaccinated subjects. Since there is no previous evidence to guide the reduction magnitude, this may be a potential limitation considering that experience with PCV13, coming from a large clinical trial including over 84,000 subjects only found a 5% (non-significant) reduction on all cause CAP and in addition, the proportion of vaccine type infection in COPD exacerbations is not established. However, recent pilot studies results showed a significant reduction on total number of exacerbations in a small group of 90 subjects 2 years post-vaccination.

Redacted

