5 ANALYSIS SYSTEMS / POPULATIONS

Considering that 37% of COPD patients will have one moderate/severe exacerbation per year, and assuming that at least 35% of patients will follow their doctor's vaccination

recommendation,³ to have at least 200 vaccinated COPD patients with moderate/severe exacerbations, a total of 1541 eligible subjects should be included in the analysis.

With 35% of patients vaccinated with PCV13, enrolling 1541 eligible subjects with COPD would provide approximately 540 patients in the PCV13 cohort and 1000 patients in the unexposed cohort.

Assuming that 37% of unexposed patients will present one moderate/severe exacerbation per year,² with 70% of the patients remaining in the study after 1 year, this sample size would provide 91% power to detect a statistically significant reduction of 10% in moderate/severe COPD exacerbations with PCV13 after 1 year. Assuming an additional 30% dropout in the second year, the study sample size would provide 91% power to detect a statistically significant reduction of 14% in moderate/severe COPD exacerbations with PCV13 after 2 years.

Time	PCV13		Unexposed		Power	Retention rate
	Sample size	% exacerbation	Sample size	% exacerbation		
Enrollment	540		1000			
1 year	378	27%	700	37%	91.43%	70% from enrollment
2 years	264	60%	490	74%	91%	70% from year 1

5.1 **FULL ANALYSIS**

The statistical analysis of this study will be carried out with all those evaluable patients with COPD, recruited by the Spanish sites participating in the study and who meet the following selection criteria:

5.1.1 **Inclusion Criteria**

Patients must meet all of the following inclusion criteria to be eligible for inclusion in the study:

1. *Aged 18 years or older at the time consent is given*
2. *Patient diagnosed with COPD (any stage, subgroups for analysis will be based on COPD severity)*
3. *Evidence of a personally signed and dated informed consent document indicating that the patient has been informed of all pertinent aspects of the study.*
4. *Ability to understand and complete the required quality of life questionnaires*
5. *Patients with at least 2 years of previous clinical history available relating to (if applicable) history of moderate/severe exacerbations, influenza and pneumococcal vaccination history, comorbidities and previous treatments*
6. *Spirometry data* (maximum 6 months old, or if not available at enrollment, to be performed as per normal clinical practice at visit 1 ± one month)*

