The Student's t test, one-way ANOVA or its non-parametric equivalents, the Mann-Mann U test or Kruskal-Wallis H test will be used to determine if statistically significant differences are observed in NEPA, NEPA Mild, NEPA Moderate, NEPA Severe and NEPA Moderate/Severe according to the severity of COPD and type of patient (exposed/unexposed). In order to determine the impact of PCV13 vaccination on exacerbations, paired data comparisons will be made between (NEPA_pre_PCV13 vs. NEPA_post_PCV13) and (NEPA_pre_PCV13 (moderate/severe) vs. NEPA_post_PCV13 (moderate/severe)), using the Student's t-test for paired data or its non-parametric equivalent, the Wilcoxon test.

In order to study which subgroups of patients obtain a greater benefit from vaccination

with PCV13 according to COPD severity, paired data comparisons will be made between (NEPA_pre_PCV13 vs. NEPA_post_PCV13) and (NEPA_pre_PCV13 (moderate/severe) vs. NEPA_post_PCV13 (moderate/severe)), in each of the four patient subpopulations established based on disease severity.

In order to determine the factors associated with the presence of an exacerbator patient, a logistic regression model will be constructed, whose dependent variable is (exacerbator/non-exacerbator patient) and, as independent variables, all those possible factors that have been significant in the univariate models ($p_{value} < 0.25$), following the methodology of Hosmer-Lemeshow.

- ❖ Vaccine exposure (PCV13 yes/no)
- ❖ COPD severity (Grade I, Grade II, Grade III, Grade IV)
- ❖ Age
- ❖ Sex
- ❖ Time since diagnosis of the disease
- ❖ Patient with stable treatment for at least three months
- ❖

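### The stated 2-year power of 91% does not follow from its own table row, which gives about 97%, and the 74% and 60% in that row have no stated basis

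*Protocol*

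**What the plan says.** The first primary objective in Protocol 7 is the effect of PCV13 "on the reduction of the risk of COPD moderate/severe exacerbations (see definitions) in adults, after 2 years of follow up".

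Protocol 8.5 enrols 540 PCV13 and 1000 control patients. It is "Assuming 37% of the control patients experiencing moderate/severe exacerbation per year" and assumes 70% retention to year 1, then 70% of those to year 2. Its table, repeated in SAP 5, reads:

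| Time | PCV13 | Control | Stated power |
|---|---|---|---|
| 1 year | 378 at 27% | 700 at 37% | 91.43% |
| 2 years | 264 at 60% | 490 at 74% | 91% |

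The protocol's text on the second row is that "the study sample size will provide 91% power to detect a statistical significant reduction of 14% on COPD moderate/severe exacerbations from PCV13 after 2-year". SAP 5 likewise claims "91% power to detect a statistically significant reduction of 14% in moderate/severe COPD exacerbations with PCV13 after 2 years".

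Neither study-size section names a test or a sidedness. SAP 4 sets p < 0.05, and Protocol 8.7 lists the Pearson chi-squared or Fisher exact test for 2x2 tables. Neither document says how 74% or 60% was obtained. Protocol 8.9 adds that the sample "aims to determine if there is a 10% significant reduction on the risk of all cause COPD exacerbations in PCV13 vaccinated subjects".

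**The concern.** The two rows have nearly the same stated power, but the 2-year row has a larger difference (14 points against 10) on 70% of the patients. A recalculation shows that these changes do not cancel.

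The 74% also looks like a yearly risk added twice. The risk of at least one exacerbation over two years is not the sum of two yearly risks unless no patient exacerbates in both years.

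The 2-year row is the power statement that matches the 2-year primary objective. As printed, a reader cannot tell whether the power, the risks or the group sizes are at fault, nor whether 74% is a deliberate assumption. The prose also calls the differences 10% and 14% without giving the scale. They are percentage points, and the relative reductions are much larger.

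**Working it through.** **Inputs.** Group sizes and risks are those in the Protocol 8.5 and SAP 5 table. Alpha is 0.05 from SAP 4, taken as two-sided (an assumption, supported by step 1).

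Pooled normal formula: power = Φ[(|d| − 1.96·SE0)/SE1], with SE0 = √{p̄(1−p̄)(1/n1 + 1/n2)} and SE1 = √{p1(1−p1)/n1 + p2(1−p2)/n2}. Fisher power is by exact enumeration of both binomials.

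**1. Reproduce the 1-year figure.** p̄ = (378×0.27 + 700×0.37)/1078 = 0.335; SE0 = 0.0301; SE1 = 0.0292.

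- Pooled: Φ[(0.10 − 0.0590)/0.0292] = Φ(1.40) = 91.9%.
- Fisher: 91.44%, against 91.43% stated. The figure reproduces.

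**2. Same method on the 2-year row.** p̄ = (264×0.60 + 490×0.74)/754 = 0.691; SE0 = 0.0353; SE1 = 0.0361.

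- Pooled: Φ[(0.14 − 0.0691)/0.0361] = Φ(1.96) = 97.5%.
- Fisher: 97.3%.
- Unpooled, arcsine, continuity-corrected, Yates and exact Pearson versions at two-sided 0.05 all lie between 97.0% and 97.6%. One-sided 0.05 gives 98.8%.

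**3. Can another reading give 91%?**

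| Change | 2-year power | Conflict with the documents |
|---|---|---|
| Two-sided alpha 0.025 | 95.1% (Fisher) | 1-year row falls to 86.0% |
| Two-sided alpha 0.01 | 90.5% (Fisher) | 1-year row falls to 77.2% |
| 62.2% v 74% | 91.0% (Fisher) | table prints 60% |
| 194 v 360 patients | 91.3% (Fisher) | 36% of enrolment (194/540), not the table's 49% (264/540) |
| 264 v 264 patients | 91.7% (Fisher) | table prints 490 controls |
| 14% read as relative (63.6% v 74%) | 83.9% (pooled) | table prints 60% |

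No single alpha fits both rows, and every other route to 91% changes a printed input.

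**4. Where could 74% and 60% come from?**

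- 2 × 37% = 74%, but 2 × 27% = 54%, not 60%.
- Independent years: 1 − 0.63² = 60.3% for controls and 1 − 0.73² = 46.7% for PCV13.
- 60% equals 74% − 14 points.
- Implied year-2 risk among those event-free in year 1: (0.74 − 0.37)/0.63 = 58.7% for controls and (0.60 − 0.27)/0.73 = 45.2% for PCV13. Protocol 8.5 states neither.

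**5. Power with derived risks, 264 v 490.**

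- Independent years, 46.7% v 60.3%: 94.4% (Fisher), 94.8% (pooled).
- Clustering lowers this. As an illustration only, a gamma frailty with mean 1 and year-1 risks held at 27% and 37% gives 42.5% v 54.0% and 84.9% power at shape 1, and 44.4% v 56.7% and 89.5% at shape 2. The distribution and shapes are my assumption. At shape 1, (2×0.37 − 0.54)/0.37 = 54% of year-1 control exacerbators exacerbate again, against (0.54 − 0.37)/0.63 = 27% of the others.

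**6. Scale.** 10/37 = 27% and 14/74 = 19% relative reduction.

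**7. Secondary: the target of 200.** The protocol abstract and SAP 5 want at least 200 vaccinated patients with exacerbations: 1541 × 0.35 × 0.37 = 199.6. That treats all 1541 as analysed. The table leaves 378 + 700 = 1078 at year 1 and 264 + 490 = 754 at year 2. Its own figures give 378 × 0.27 = 102 such patients at year 1 and 264 × 0.60 = 158 at year 2.

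**The case against.** The strongest reply is that the error is conservative and changes no design decision. The 1541 comes from the target of 200 vaccinated patients with exacerbations, and power is then quoted for that size. Protocol 8.9 describes the sample in terms of a 10% reduction, which is the 1-year effect, and that row is correct. This stands as far as it goes: on the printed inputs the study has more power than it claims. But the objective is set at 2 years, and the reassurance holds only if 74% and 60% are sound.

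A second reply is that planning risks may be chosen freely and the documents never say that 37% was doubled. Protocol 6 notes that "as COPD progresses, exacerbations become more frequent", so a higher risk in year 2 is possible. That is fair, and doubling remains an inference. The same section also says "Nonpneumonic COPD exacerbations predict increased risk of subsequent exacerbations", which points to repeat events in the same patients and so to a lower 2-year risk. Protocol 8.5 invokes neither argument. What stands is a missing justification rather than a proven wrong risk.

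Third, a slip in group size could be the cause, since 264 per group gives 91.7%. If so, the risks are not implicated in the power error. The cause is unknown, but the row is still wrong as printed.

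**Conclusion.** The concern holds. On its own inputs the 2-year row gives about 97% power, not 91%, in both documents. This rests only on two-sided 0.05, which the 1-year row supports.

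The missing basis for 74% and 60% is a reporting gap. Its effect depends on what was meant: about 97% if the printed risks are kept, about 94% if 27% and 37% apply independently in each year, and lower with clustering (85% to 90% in the illustration). The stated 91% could therefore be too low or too high.

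All these figures are for a two-group comparison of proportions. They are not the power of the before/after analysis in SAP 8.2.3.1, which says: "In order to determine the impact of PCV13 vaccination on exacerbations, paired data comparisons will be made". The scale wording and the 200-patient target are lesser points.

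**What to change.** In Protocol 8.5 and SAP 5, do one of the following:

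- Keep 60% v 74%, correct the 2-year power to about 97%, and state the reason for each risk (for example, a rising risk in year 2).
- Replace both risks with values derived from the yearly risks under a stated assumption, and recompute. With independent years and 27% continuing into year 2, that is 46.7% v 60.3% and about 94%, with a note that clustering in the same patients lowers it.

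In either case, name the test and sidedness and say that the power is for the two-group comparison of proportions. Write percentage points for the 10 and 14 in Protocol 8.5, Protocol 8.9 and SAP 5, with the relative values (27% and 19%) alongside. Reconcile the 1541 and the 200 target in the protocol abstract and SAP 5 with the table's attrition.

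The cost is a text correction in Protocol 3, 8.5 and 8.9 and SAP 5, with no extra patients and no design change.

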#### **8.6. Data management**

- Study data will be collected by site staff in an electronic CRF. Details on management of data included in the electronic CRF will be included in the Data Management Plan.

Redacted

- In accordance with quality control criteria on collecting information, a monitor designated by Pfizer will contact the study investigator to supervise study conduct and protocol compliance according to the Monitoring Plan. To record study monitoring, the monitor will complete the Contact Report or the Monitoring Report.
- Data management system procedures including data transfer process from raw data on the electronic CRF until a 'clean' database is obtained will be described in the Data Management Plan.

## **8.7. Data analysis**

Depending on recruitment and data availability an interim analysis may be performed after the first year, if at least 75% of subjects included have completed one year of follow up.

- To determine the impact of PCV13 vaccination, the incidence of exacerbations will be determined 2 years after the inclusion in the study and will be compared with the incidence 2 years before the study (2 years of clinical history required including records of previous moderate/severe exacerbations, influenza and pneumococcal vaccination history comorbidities and previous treatments)
- A descriptive analysis of all variables will be performed. Qualitative variables will be analyzed by absolute and relative frequencies. Quantitative variables will be studied by the usual centralization and dispersion measures (mean, median, standard deviation, confidence intervals, minimum, maximum and interquartile range).
- For comparison of independent samples, the Pearson chi-squared test or the exact Fisher test for 2x2 tables or likelihood ratio for mXn tables, for qualitative variables, will be used. The Student's t test, one-way ANOVA or its non-parametric equivalent U-Mann-Mann, H-Kruskal-Wallis for quantitative variables will be used.
- For comparison of paired samples, the McNemar's test will be used for qualitative variables and Student's t test or Wilcoxon's test for quantitative variables.
- A multivariate logistic regression analysis will be performed, in order to identify risk factors associated with exacerbations. Exacerbations existence (yes/no) will be used as dependent variable. Vaccination with PCV13 and statistically significant variables in the univariate model, will be used as possible risk factors: demographic characteristics, influenza vaccination, smoking habit, etc. In addition, potential confounding variables will be considered: phenotype, comorbidities, COPD severity, FEV1 (no control possible based on the study design)
- Appropriate tests will be performed accordingly to determine if the necessary requirements are fulfilled for the use of parametric contrasts.
- Estimates will be performed with a 95% confidence interval. The SPSS statistical package version 19.0 or later will be used.

Redacted

Detailed methodology for summary and statistical analyses of data collected in this study will be documented in a Statistical Analysis Plan (SAP), which will be dated, filed and maintained by the sponsor. The SAP may modify the plans outlined in the protocol; any major modifications of primary endpoint definitions or their analyses would be reflected in a protocol amendment.

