## **CALENDAR**

- Protocol submission to IEC and to the Ministry of Health is expected to be done by September 2016 in order to obtain approvals in November 2016.
- Financial agreements with the sites are expected to be obtained from December 2016 to February 2017.
- Recruitment of participant subjects is expected to start (FSFV) in January 2017. The recruitment will end in January 2019.
- Database is expected to be completed and closed by April 2019. Data analysis is expected by September 2019. Study results are expected by October 2019.

Pneumococcal 13-valent conjugate vaccine (diphtheria CRM197 Protein)

B1851177

NON-INTERVENTIONAL STUDY PROTOCOL

31 October 2016

---

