There are two types of pneumococcal vaccines, a 23 valent polysaccharide vaccine and a 13 valent conjugate vaccine. The 23-valent pneumococcal polysaccharide vaccine (PPV23) is approved and recommended for use in persons  $\geq 2$  years of age for the prevention of pneumonia and pneumococcal disease. In the past decades many studies have evaluated the effect of PPV23 in adults, and effectiveness in preventing IPD has been reported, but with a short duration of protection, and limited impact on the total burden of disease even in countries with high uptake. Regarding the prevention of noninvasive pneumococcal pneumonia, the most common clinical presentation of the disease in adults, studies assessing the effectiveness of PPV23 show inconsistent results. Moreover, the available studies focused specifically on COPD patients, do not show a clear effect on any of the outcomes evaluated (developing pneumonia or acute exacerbations).

The 13 valent pneumococcal conjugate vaccine was approved by the EMA for the prevention of IPD in adults  $\geq 50$  in 2011, and subsequently in 2013 for adults  $\geq 18$  years of age, based on immunogenicity studies. Following the publication of the results of the CAPiTA study in 2015, showing the efficacy of the vaccine for the prevention of bacteremic (45.6%) and non-bacteremic (45%) pneumococcal pneumonia, and IPD (75%) caused by PCV13 serotypes in subjects  $\geq 65$  years old, the EMA approved the indication for the prevention of pneumonia in adults aged  $\geq 18$  years.

Recent exploratory studies have shown a beneficial effect of PCV13 in reducing the number of exacerbations in COPD and other respiratory diseases. Results from a group of 90 COPD patients vaccinated with PCV13 and followed for 2 years in Spain, showed a reduction of 50% in the number of severe exacerbations in the second year after immunization. A prospective comparative open label study carried out in Russia, evaluating PCV13 safety and effectiveness to prevent CAP in COPD patients compared with non-vaccinated patients, found in a group of 25 patients a 4.8-fold reduction in the incidence of exacerbations one year after vaccination.

The limitations of these preliminary results require larger studies, specifically designed for this purpose, to assess which sub-groups might benefit most from this preventive approach.

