## **Study procedures**

Subjects identified with COPD will be informed about the study and invited to participate by investigators at the time of their routine control visits. All therapies will be prescribed according to the updated National COPD Guidelines (GesEPOC) indicating among other therapies active reduction of risk factors, influenza and pneumococcal vaccination (with PCV13) in all patients with mild, moderate or severe COPD. All the patients will be counselled to stop smoking and advised on life-style modifications. Any vaccination will be prescribed according to clinical practice and not related to the decision to include the subjects in the study. Subjects may be vaccinated before or after inclusion in the study.

Study will include periodic scheduled visits for all patients, to complete a total follow up of 2 years (see Table 1).

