### **8.2.1. Inclusion criteria**

Patients must meet all of the following inclusion criteria to be eligible for inclusion in the study:

1. Patient  $\geq 18$  years diagnosed with COPD (any stage, the subgroups for the analysis would be based on COPD severity grade)

Redacted

2. Evidence of a personally signed and dated informed consent document indicating that the patient (or a legally acceptable representative) has been informed of all pertinent aspects of the study.
3. Ability to understand and complete the required QoL questionnaires
4. At least 2 years of clinical history available that includes records of previous moderate/severe exacerbations, influenza and pneumococcal vaccination history comorbidities and previous treatments.
5. Spirometry data\* (maximum 6 months old, or if not available at enrollment, to be performed as per normal clinical practice at visit 1 +/- one month)

\*Subjects with FEV1 <40 should be less than 20% of the total study population (related to the microbiological etiology dependent on severity)

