### **8.2.2. Exclusion criteria**

Patients meeting any of the following criteria will not be included in the study:

1. Impossibility to perform prospective follow up
2. Present any immunocompromising condition
3. Present any other respiratory diseases as co-morbidity (subjects with overlap syndromes COPD-asthma will be excluded. Mixed phenotype defined as: symptoms of increased variability of airflow and incompletely reversible airflow obstruction)

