**TABLE 1. FOLLOW UP VISITS**

	Visit	0	1	2	3	4	5
	Month	0	1	6	12	18	24
Verification of inclusion/exclusion criteria		X	X	X	X	X	X
Informed consent signature		X					
Demographic variables		X					
Exacerbations and smoking history		X	X	X	X	X	X
Clinical history (hospital and/or primary care)		X					
Performance or verification of recent spirometry		X			X		X
Completion of QOL test		X			X		X
Treatment and vaccination recommendations adjustment (as per normal clinical practice)		X			X		X
Telephone Follow up (if applicable)				X		X	
PCV13 vaccination record			X		X		X
Influenza vaccination record			X		X		X
Updated treatment record			X		X		X

**Definitions:**

- COPD exacerbations are defined as a complex of two or more respiratory symptoms (worsening dyspnea, cough, sputum production, chest tightness, or wheezing) related to the underlying COPD, with duration of 3 days or more, that require a change in treatment.
  - *Treatment changes* include acute treatment with antibiotics and/or steroids, or an addition of new maintenance bronchodilator.
  - *Mild exacerbations* are those that require new prescription of bronchodilator only
  - *Moderate exacerbations* are those that require antibiotics and/or systemic corticosteroids without hospitalization,
  - *Severe exacerbations* are those that lead to hospitalization.
- The onset date of exacerbations is defined by the onset of the first recorded symptom.
- Exacerbations that occur within 7 days of onset of a prior exacerbation are counted as a single exacerbation

A subject presenting with exacerbation, will be considered as vaccinated at least 15 days after receiving immunization

Redacted

- Immunosuppression:
  - Lymphoma/Leukemia
  - Another neoplasm subjected to immunosuppressing treatments
  - Organ transplant with its corresponding immunosuppressing treatment
  - Leukopenia<1.000/mm; neutropenia<500/mm
  - Patients infected by Human Immunodeficiency Virus (HIV)
  - Congenital immunodeficiency
  - Diseases that requires continuous treatment with systemic corticosteroids administration for more than 14 days (prednisone at doses> 15 mg/day or other equivalent preparations), or cytotoxic agents during the previous six months.

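### Protocol 8.7 anchors its before/after comparison on inclusion instead of the PCV13 dose; the SAP moves the split to the dose without a matching amendment or assured pre-dose records

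*Protocol*

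**What the plan says.** - **Comparison in the protocol.** Section 8.7 sets out to determine the impact of PCV13 from incidence that "will be determined 2 years after the inclusion in the study and will be compared with the incidence 2 years before the study". The vaccination date plays no part.
- **Timing of the dose.** Protocol 8.2 (Study procedures) states: "Subjects may be vaccinated before or after inclusion in the study". The three exclusion criteria in 8.2.2 do not mention earlier PCV13, and neither does any inclusion criterion set a limit on it.
- **History required.** Protocol 8.2.1, criterion 4, asks for "At least 2 years of clinical history available that includes records of previous moderate/severe exacerbations". SAP 5.1.1, criterion 5, asks for "Patients with at least 2 years of previous clinical history available relating to (if applicable) history of moderate/severe exacerbations". Both are conditions of entry. Neither is tied to the dose.
- **When a patient counts as vaccinated.** The definitions under Protocol Table 1 say that a patient with an exacerbation "will be considered as vaccinated at least 15 days after receiving immunization". No end date is given.
- **Comparison in the SAP.** Section 8.2.3.1 drops the inclusion-anchored windows. It pairs each vaccinated patient's exacerbation rate before PCV13 (time from COPD diagnosis to the dose) with the rate after it (time from the dose to last follow-up), overall and by GOLD grade.
- **Amendments.** Protocol 8.7 lets the SAP modify the plan but says that major changes to primary endpoint definitions or their analyses would be reflected in a protocol amendment. Protocol section 4 lists none.

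**The concern.** A before/after comparison can show a vaccine effect only if its dividing line separates unvaccinated from vaccinated time. Inclusion does so only for patients vaccinated at about Visit 0. Old doses are possible on the protocol's own dates. Section 6 puts adult approval at 2011 (age 50 and over) and 2013 (age 18 and over), and the Calendar says: "Recruitment of participant subjects is expected to start (FSFV) in January 2017". The earliest window before the study therefore opens about January 2015, after both approvals.

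This comparison serves the first primary objective. If it is run as 8.7 describes, a null result could not be told apart from a misplaced dividing line. If it is run as the SAP describes, the line is in the right place, but the time before it may not be covered by the records that eligibility assures.

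**Working it through.** **1. The plan's own figures.** The plan gives no effect size or power for the before/after comparison. Its nearest figures are for vaccinated versus unvaccinated patients (Protocol 8.5): 27% of 378 versus 37% of 700 at 1 year, stated power 91.43%. With a two-sided 5% test:

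- pooled risk = (378 × 0.27 + 700 × 0.37)/1078 = 0.335
- SE under no difference = √[0.335 × 0.665 × (1/378 + 1/700)] = 0.0301
- SE under the stated risks = √[0.27 × 0.73/378 + 0.37 × 0.63/700] = 0.0292
- power = Φ[(0.10 − 1.96 × 0.0301)/0.0292] = Φ(1.40) = 91.9%

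This reproduces the stated figure closely. The 2-year power (60% of 264 versus 74% of 490, stated 91%) comes out at 97.5% by the same formula. That is a separate matter and nothing below uses it.

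**2. Dilution under Protocol 8.7, dose before inclusion.** Let r be the true rate ratio, vaccinated to unvaccinated, and s the vaccinated share of the 24-month window before the study. For a dose m months before inclusion, s = min(m, 24)/24. The apparent after/before ratio is r/[(1 − s) + s·r]. Two assumed values of r come from the plan's figures:

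- r = 27/37 = 0.730, the 1-year risks used as rates
- r = ln(1 − 0.60)/ln(1 − 0.74) = 0.680, the 2-year risks under a constant rate

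The 15-day rule is ignored here as small.

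| Dose before inclusion | s | Ratio, r = 0.730 | Apparent reduction | Ratio, r = 0.680 |
|---|---|---|---|---|
| 0 months | 0 | 0.730 | 27% | 0.680 |
| 6 months | 0.25 | 0.783 | 22% | 0.739 |
| 12 months | 0.50 | 0.844 | 16% | 0.810 |
| 18 months | 0.75 | 0.915 | 8% | 0.895 |
| 24 months or more | 1 | 1.000 | 0% | 1.000 |

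For example, at 12 months: 0.730/[(1 + 0.730)/2] = 0.730/0.865 = 0.844.

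The same rows describe a group in which a share s was vaccinated at least 24 months before entry and the rest at inclusion. The documents do not give that share, so the whole range from 0 to 1 is open.

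**3. Dilution under Protocol 8.7, dose after inclusion.** Now the later window contains unvaccinated time. For a dose m months after inclusion the apparent ratio is m/24 + (1 − m/24)·r. With r = 0.730, doses at 6, 12 and 18 months give 0.797, 0.865 and 0.932, so the 27% reduction appears as 20%, 14% and 7%.

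**4. The SAP's comparison.** Splitting at the dose makes s = 0 and restores r, so steps 2 and 3 do not apply to it. What remains is whether the numerator and denominator cover the same time. The assured pre-dose record is max(0, 24 − m) months for a dose m months before inclusion, while the denominator is all time from diagnosis to dose. Take a hypothetical patient diagnosed in January 2009 and enrolled in January 2017:

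- dose in January 2014: denominator 60 months, assured pre-dose record 0 months
- dose in January 2016: denominator 84 months, assured record 12 months, 12/84 = 14%
- dose in January 2017: denominator 96 months, assured record 24 months, 24/96 = 25%

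If the rate is constant and events outside the assured record go uncounted, the pre-dose rate is scaled down by these fractions. They are the worst case, because sites may hold longer records.

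The SAP's fallback start of 2 years before inclusion, for an unknown diagnosis date, is attached to overall follow-up time. If it were also used for pre-dose time, a patient vaccinated earlier than that would have zero or negative time.

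**The case against.** The strongest reply is that the SAP governs the analysis, Protocol 8.7 allows it to modify the plan, and it already splits at the PCV13 date. This largely stands. A reader might infer from the table that the planned paired test will be diluted by these amounts. The documents do not support that, because the figures describe only the comparison in Protocol 8.7. Two gaps remain: the documents define different before/after comparisons for a primary objective with no amendment, and the SAP moved the split without tying the history to the dose.

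Other stronger readings also go too far:

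- **That the contrast is empty for everyone vaccinated before entry.** It is empty only for doses about 24 months or more before Visit 0. For a dose a few weeks before, the dilution is trivial.
- **That old doses are common.** The approval dates show only that they are possible. The sample size rests on patients following a pulmonologist's recommendation, which does not settle the timing either way.
- **That the net bias is known to run toward no effect.** Window dilution does run that way. But patients vaccinated earlier enter only if they survived and stayed under care, and that selection can lower observed post-dose rates and favour the vaccine. The documents do not allow the two to be netted.
- **That the cohort comparison fails with it.** Vaccinated versus unvaccinated patients is the stated design and the basis of the power calculation. It is a different analysis.

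SAP 8.2.3.5 does tabulate vaccination history, including conjugate vaccine, so prior use will be partly described. Neither document separates patients vaccinated before entry from those vaccinated during the study in the effectiveness analyses.

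**Conclusion.** The point holds in two parts. First, Protocol 8.7 uses the wrong dividing line for any patient not vaccinated close to inclusion. With an assumed 27% true reduction, it would show 16% for a dose 12 months before entry and 0% for 24 months or more. The overall size cannot be stated, because the timing of vaccination is not given. Second, the SAP corrects the dividing line, but no protocol amendment reflects the change, and its pre-dose person-time can exceed the assured records. A patient vaccinated more than 2 years before entry may have no assured pre-dose record at all, which would understate the pre-dose rate and hide benefit.

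The first part rests on the text and needs no assumed figure except for the illustration. The second assumes that some sites' records do not reach back to diagnosis. This should be fixed before analysis. It does not show that the study as a whole is invalid.

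**What to change.** 1. **Protocol 8.7, by amendment:** replace the windows around inclusion with windows anchored on the PCV13 date, applying the protocol's 15-day rule, so that protocol and SAP describe the same comparison.
2. **SAP 8.2.3.1:** limit pre-PCV13 person-time to the period with documented records, for example the 2 years before the dose, and count exacerbations over that same period. Restrict the paired comparison to patients with that history. Make this an analysis-set rule and leave the eligibility criteria as they are.
3. **Both documents:** report patients vaccinated before Visit 0 separately from those vaccinated during the study, and keep both groups in the vaccinated-versus-unvaccinated follow-up comparison.

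The cost is wording in two documents. SAP 8.2.1 already refers to the date of pneumococcal vaccination, so no new item should be needed for the anchor. The real price is fewer patients in the paired comparison; those removed lack the documented pre-dose baseline that the comparison needs. State how many are removed.
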